12.4.3.3 Interim Analyses

No interim analysis is planned.

12.4.3.4 Statistical analyses

A descriptive analysis will be conducted on the following parameters:

- Patients and transplant characteristics
- Primary and secondary endpoints

The toxicities rate will be calculated and will be given with their 95% confidence intervals.

The probabilities of survival will be estimated by the Kaplan-Meier method and by calculating the cumulative incidences for relapse/progression, and non-relapse mortality incidence.

12.4.3.5 Determination of sample size

The aim of this study is to assess whether ATO allows improving response rate at 6 months after the diagnosis of chronic GVHD from 60% to 85%.

For the sample size calculation in this trial, an A'Hern one stage design has been used (ref 1).

- Let P_0 be the smallest response rate, if true, implies that the role of ATO is too low and therefore the present schedule does not warrant further investigation. In the present trial, P_0 has been taken as 60%.
- Let P_1 be the highest response rate which, if true, implies that the feasibility is sufficiently high and therefore the current schedule warrants further investigation in clinical trials. In the present trial, P_1 has been taken as 85%;
- Let α be the accepted probability of recommending for further investigation a regimen with a true discontinuation rate at least equal to P_0 . In the present trial, α has been taken as 0.05.
- Let β be the accepted probability of rejecting for further investigation a regimen with a true discontinuation rate less than P_1 . In the present trial, β has been taken as 0.20.

The required number of eligible patients is 21. To compensate for a dropout of 10%, 24 patients are planned to be included.

12.5 CHANGES IN THE CONDUCT OF THE STUDY OR PLANNED ANALYSIS

Any changes to the analyses described in the protocol or in approved versions of this plan will be fully documented in a specific part of the clinical study report of the study.

10. PATIENTS

10.1 DISPOSITION OF PATIENTS

All patients screened and receiving at least one infusion of ATO will be accounted for.

Derivation

Derived variables	Definition
Study completed	Yes, if the patient is present in the study at M12 No, if the patient is not present in the study at M12

The following table will be then presented:

	Analysis set (N=XX)
Study completed	n/N (XX.XX%)
Withdrawal of informed consent	n/N (XX.XX%)
Lost to follow-up	n/N (XX.XX%)
Occurrence of AE/SAE requiring premature discontinuation	n/N (XX.XX%)
Inclusion criteria not met requiring premature discontinuation	n/N (XX.XX%)
Other reason	n/N (XX.XX%)

10.2 PROTOCOL DEVIATIONS

Protocol deviations will be summarized as follows:

Analysis set (N=XX)		
	Number of patients	Number of deviations
No deviation	n/N (XX.XX%)	n
Major deviation	n/N (XX.XX%)	n

11. EFFICACY EVALUATION

11.1 ANALYSES POPULATIONS

Every patient included in the study and who has received at least one infusion of ATO will be taken into account at time of data analysis.

The number of patients included who did not receive any infusion of ATO will be reported as well as the reason for not receiving ATO.

The following analyses populations will be considered:

- The safety population consists of all patients included in the study for whom there is any evidence that they used at least one ATO injection.
- The Full Analysis Set (FAS) population consists of included subjects who completed their first cycle of ATO and for whom the response at Week 6 after diagnosis of chronic GvHD has been evaluated.
- The Per Protocol (PP) population will exclude FAS patients with any major protocol deviations that may impact the efficacy analysis. The exclusion of patients from the PP population will be determined during the final data review meeting. Reason(s) for exclusion will be documented for each patient.

The following table will be presented:

Analysis set (N=XX)	
Safety Population	n/N (XX.XX%)
Full Set Analysis Population	n/N (XX.XX%)
Per Protocol Population	n/N (XX.XX%)

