### **10.2. Analyses data set**

Every patient included in the study and who has received at least one infusion of ATO will be taken into account at time of data analysis.

Patients who do not receive any injection of ATO will not be analyzed and will be replaced to obtain 24 patients provided in the statistical analysis.

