### **10.4.2. Efficacy failure**

Efficacy failure is defined as early treatment failure is first checked at week 6 post ATO. Treatment failure will be defined as:

- Required initiation of a new systemic treatment for chronic GvHD before week 6
- Recurrent or progressive malignancy before week 6
- Death before week 6

Failure-free survival (FFS), is defined as death, recurrent or progressive malignancy, or the initiation of a new systemic treatment for chronic GvHD (defined below).

From the perspective of the patient, secondary therapy and death have very different significance with respect to efficacy, since the need for secondary therapy does not inevitably lead to death. From the perspective of the clinical trial, however, both events indicate that the study-drug did not have the desired efficacy.

Discontinuation of treatment with study-drug because of toxicity will not be categorized as efficacy failure in and of itself, since it is possible that a short period of treatment with the study-drug could have long lasting benefit ultimately resulting in efficacy success. After a toxic study-drug outcome, patients will be followed for any subsequent initiation of secondary systemic treatment development of recurrent malignancy, death from causes other than recurrent malignancy, or dropout with lack of follow-up information. Any of these events occurring during primary treatment for chronic GvHD will be categorized as efficacy failure.

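### The SAP's full analysis set drops treated patients who do not complete cycle 1 or lack a Week 6 evaluation, so the all-treated analysis that both documents state is carried out in no efficacy table

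*SAP*

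**What the plan says.** Protocol 10.2 sets the analysis population as every included patient "who has received at least one infusion of ATO will be taken into account at time of data analysis". Only patients with no infusion are removed, and they are replaced to reach 24. The SAP synopsis repeats this, and SAP 11.1 opens the same way: "Every patient included in the study and who has received at least one infusion of ATO".

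SAP 11.1 then defines three sets. The safety population is all treated patients. The FAS is restricted to those "who completed their first cycle of ATO and for whom the response at Week 6 after diagnosis of chronic GvHD has been evaluated", and the per-protocol (PP) set is the FAS less major deviations.

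Protocol 10.4.2 says that "early treatment failure is first checked at week 6 post ATO" and lists as failures "Required initiation of a new systemic treatment for chronic GvHD before week 6", recurrent or progressive malignancy before week 6, and "Death before week 6". On toxicity it says: "Discontinuation of treatment with study-drug because of toxicity will not be categorized as efficacy failure in and of itself". Such patients are followed for secondary treatment, relapse, death or dropout, and "Any of these events occurring during primary treatment for chronic GvHD will be categorized as efficacy failure".

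The primary response (SAP 11.4.1.1) and failure-free (FFS), progression-free (PFS) and overall survival (OS) (SAP 11.4.2.2) are tabulated on the FAS. The lists in SAP 14.1 and 14.2 add only PP versions and the sensitivity analyses of SAP 11.4.1.2.

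**The concern.** Both FAS conditions are met or missed after treatment starts, and both can depend on outcome. A patient the protocol calls a failure can therefore disappear from the denominator instead of counting against the drug. The trial has one arm, 24 patients and a fixed 60% benchmark, so no control arm shares the bias and one or two patients can decide the result.

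Survival has a related problem. FFS and OS are timed from the first infusion, but a FAS patient must have lived to the end of cycle 1, and on a strict reading to the Week 6 evaluation. The curves then contain early time in which no included patient could die.

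**Working it through.** **1. Who leaves the FAS**

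- Death before cycle 1 is complete: always.
- Death after cycle 1 but before Week 6: leaves unless it is scored as an evaluated Week 6 failure. Protocol 10.4.2 and the early-failure definition in the synopsis would allow that scoring; the SAP does not say so.
- Relapse, new systemic treatment or a toxicity stop: only if it prevents cycle 1 completion or the Week 6 evaluation.
- Delay alone: need not exclude. Protocol 7.3.2.1 reschedules cancelled infusions and Protocol 8.1 postpones the visit.

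**2. Whether another analysis brings them back**

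The sensitivity analyses in SAP 11.4.1.2 use the PP set, the computed response, or omit three named patients. None covers all treated patients. The optional missing-equals-failure imputation in SAP 12.4.3.2 concerns missing M6 assessments, not patients outside the FAS. Safety-population tables show deaths and secondary treatment but give no efficacy estimate.

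**3. The plan's own design figure**

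Inputs (Protocol 10.7, SAP 12.4.3.5): P0 = 0.60, P1 = 0.85, n = 21, success if at least 17 respond, 10% dropout.

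- P(Bin(21, 0.60) ≥ 17) = 0.037; P(Bin(21, 0.85) ≥ 17) = 0.803.
- 21/0.90 = 23.3, rounded up to 24.

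The design reproduces as a one-sided exact 0.05 test. The protocol gives a cut-off only for 21, so for other sizes I use the smallest count with one-sided exact p ≤ 0.05. SAP 11.4.1.1 instead uses a 95% Clopper-Pearson interval. Its text rejects when the lower bound is below 60%; I read it as above 60%.

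Cut-offs (one-sided / Clopper-Pearson): n = 21: 17/18; n = 22: 18/19; n = 23: 19/19; n = 24: 19/20.

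**4. Single results, 24 treated, excluded patients all failures**

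| Excluded | FAS result | Same responders, all treated | Rule |
|---|---|---|---|
| 1 | 19/23, lower bound 61.2%: passes | 19/24, 57.8%: fails | Clopper-Pearson |
| 3 | 17/21 = 81.0%, p = 0.037: passes | 17/24 = 70.8%, p = 0.192: fails | one-sided exact |

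Under the one-sided test one excluded failure cannot flip the result. Two can: 18/22 (p = 0.027) against 18/24 (p = 0.096).

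**5. Type I error**

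Let e be the share excluded (assumed) and r the response rate among the excluded. With a true all-treated rate of 60%:

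FAS rate = (0.60 − e·r)/(1 − e)

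Error = Σ over k of P(Bin(24, e) = k) × P(Bin(24 − k, FAS rate) ≥ cut-off for 24 − k)

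For e = 10%, r = 0: FAS rate = 0.60/0.90 = 0.667.

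| Scenario | One-sided exact | Clopper-Pearson |
|---|---|---|
| No exclusions | 0.040 | 0.013 |
| e = 10%, r = 0 | 0.095 | 0.054 |
| e = 10%, r = 30% | 0.053 | 0.028 |
| e = 10%, r = 60% | 0.027 | 0.013 |

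With r = 0 and e = 5% or 15%, the errors are 0.054 or 0.168 (one-sided) and 0.029 or 0.106 (Clopper-Pearson).

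**6. Survival**

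Three deaths before the end of cycle 1 and none later: OS at M6 is 21/21 = 100% in the FAS and 21/24 = 87.5% in all treated.

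**The case against.** A reader might infer that the SAP plans no all-treated efficacy analysis. That goes too far. The synopsis and SAP 11.1 say all treated patients are taken into account, and the synopsis and SAP 12.4.3.4 promise a descriptive analysis of the primary and secondary endpoints. The supportable statement is that the SAP contradicts itself and its tables follow the narrower definition.

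A reader might also infer that every early failure is lost, or that excluded patients are all failures. Neither follows. A failure who completes cycle 1 and is evaluated stays in, delays are accommodated, and the protocol does not treat a toxicity stop as a failure in itself. All non-responders is therefore the worst case. At 30% response among the excluded, Clopper-Pearson error stays at or below 0.041 for exclusion rates up to 15%.

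A third tempting reading is that PFS is inflated by lost deaths, like OS and FFS. SAP 11.4.2.2 b derives PFS from progression alone, so an excluded early death hides no event there; only an excluded early progression would. SAP 8.2.2 words PFS differently, but the derivation drives the table.

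Finally, the three extra patients might be thought to cover early failures. Neither sample-size section says that early failures count as dropouts. These points limit the size of the bias; they do not resolve the conflict between the FAS and the stated population.

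**Conclusion.** The point holds as a contradiction with a potential bias, and should be settled before the analysis. One excluded failure can reverse the conclusion under the Clopper-Pearson rule, and two can under a one-sided exact test. At an assumed 10% exclusion, error at least doubles if all excluded are non-responders, and there is no inflation if they respond like the rest. If nobody is excluded, the response and survival estimates are unchanged. The documents give no early-failure rate, so the 5% to 15% range is an assumption and no actual bias is shown. Population counts and listings would reveal exclusions but would not correct the estimates.

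**What to change.** - Define the FAS as all included patients with at least one ATO infusion, and use it for the primary response, FFS, PFS and OS.
- Count the early failures of Protocol 10.4.2 as non-responders and FFS events, and deaths as OS events. Classify toxicity stops by later outcome, as that section requires.
- Count treated patients who withdraw or are lost before any recorded response as non-responders in the primary analysis, instead of the case-by-case most plausible outcome of SAP 12.4.3.2.
- State whether Protocol 10.4.1 or 10.4.2 governs dropout after a recorded response; the two can be read differently.
- Date Week 6 from the first infusion, as Protocol 9.3 counts weeks, not from diagnosis.
- Keep the current set as a labelled sensitivity analysis (cycle-1 completers evaluable at Week 6), and say how a death between the end of cycle 1 and Week 6 is handled there.
- State the cut-off for 24: at least 19 at one-sided 0.05 (error 0.040, power 0.861 at 85%), or at least 20 under the Clopper-Pearson rule (error 0.013, power 0.713).

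The cost is SAP wording and a changed population flag, with no new data. If 85% holds in all treated patients, power does not fall against 21 (0.803 to 0.861 one-sided; 0.611 to 0.713 Clopper-Pearson). The reported response rate may be lower. If 85% holds only outside 10% excluded failures, the all-treated rate is 0.85 × 0.90 = 76.5%, and power falls to 0.491 (at least 19) or 0.303 (at least 20).

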11.2 DEMOGRAPHIC AND OTHER BASELINE CHARACTERISTICS

11.2.1 Demographic characteristics

Derivation

Derived variable	Definition
Age at inclusion (in years)	Year of inclusion – Year of birth

The following table will be presented:

Variable	Statistics / Modality	Safety Population (N = XX)
Gender	Male	n/N (XX.X%) n/N (XX.X%) n
	Female	
	Missing	
Age at inclusion (in years)	N (N Missing)	XX (XX)
	Mean ± SD	XX.X ± XX.X
	Median [Min ; Max]	XX [XX ; XX]
Contraception	Yes	n/N (XX.X%) n/N (XX.X%) n
	No	
	Missing	
Weight (kg)	N (N Missing)	XX (XX)
	Mean ± SD	XX.X ± XX.X
	Median [Min ; Max]	XX [XX ; XX]
Height (cm)	N (N Missing)	XX (XX)
	Mean ± SD	XX.X ± XX.X
	Median [Min ; Max]	XX [XX ; XX]
Cardiac frequency (beats/min)	N (N Missing)	XX (XX)
	Mean ± SD	XX.X ± XX.X
	Median [Min ; Max]	XX [XX ; XX]
Systolic arterial pressure (mmHg)	N (N Missing)	XX (XX)
	Mean ± SD	XX.X ± XX.X
	Median [Min ; Max]	XX [XX ; XX]
Diastolic arterial pressure (mmHg)	N (N Missing)	XX (XX)
	Mean ± SD	XX.X ± XX.X
	Median [Min ; Max]	XX [XX ; XX]

Temperature (°C)	N (N Missing) Mean ± SD Median [Min ; Max]	XX (XX) XX.X ± XX.X XX [XX ; XX]
O2 saturation (%)	N (N Missing) Mean ± SD Median [Min ; Max]	XX (XX) XX.X ± XX.X XX [XX ; XX]

11.2.2 Baseline characteristics

Derivation

Derived variable	Definition
Time from transplant to chronic GVHD (in days)	Assessment date - Date of the first allogeneic stem cell transplantation +1
Daily steroid dose (Prednisone): mg/kg/d	Considering the treatment line when the baseline occurs, the daily dose is calculated as: Dose*frequency/weight The frequency can be: once a day, twice a day, 1 day on 2 etc.
Daily cyclosporine dose	Considering the treatment line when the baseline occurs, the daily dose is calculated as: Dose*frequency The frequency can be: once a day, twice a day, 1 day on 2 etc.

The following table will be presented:

Variable	Statistics / Modality	Safety Population (N = XX)
Significant current disease	No	n/N (XX.X%)
	Yes	n/N (XX.X%)
	Missing	n
Donor / Recipient features	Modality 1	n/N (XX.X%)
	Modality 2	n/N (XX.X%)

	Modality n	n/N (XX.X%)
	Missing	n
Conditioning regimen		
Conditioning regimen	Modality 1	n/N (XX.X%)
	Modality 2	n/N (XX.X%)

	Modality n	n/N (XX.X%)
	Missing	n
Previous infusion of DLI		
DLI	No	n/N (XX.X%)
	Yes	n/N (XX.X%)
	Missing	n
Time from transplant to GVHD		
Time from transplant to chronic GVHD (in days)	N (N Missing)	XX (XX)
	Mean ± SD	XX.X ± XX.X
	Median [Min ; Max]	XX [XX ; XX]
Concomitant disease		
Current disease?	No	n/N (XX.X%)
	Yes	n/N (XX.X%)
	Missing	n
Haematology		
Leucocytes	N (N Missing)	XX (XX)
	Mean ± SD	X.XX ± X.XX
	Median [Min ; Max]	X.X [X.X ; X.X]
Neutrophils	N (N Missing)	XX (XX)
	Mean ± SD	X.XX ± X.XX
	Median [Min ; Max]	X.X [X.X ; X.X]
Lymphocytes	N (N Missing)	XX (XX)
	Mean ± SD	X.XX ± X.XX
	Median [Min ; Max]	X.X [X.X ; X.X]

Monocytes	N (N Missing) Mean ± SD Median [Min ; Max]	XX (XX) X.XX ± X.XX X.X [X.X ; X.X]
Eosinophils	N (N Missing) Mean ± SD Median [Min ; Max]	XX (XX) X.XX ± X.XX X.X [X.X ; X.X]
Hemoglobin	N (N Missing) Mean ± SD Median [Min ; Max]	XX (XX) XX.XX ± XX.XX XX.X [XX.X ; XX.X]
Platelets	N (N Missing) Mean ± SD Median [Min ; Max]	XX (XX) XXX.X ± XXX.X XXX [XXX ; XXX]
aPTT	N (N Missing) Mean ± SD Median [Min ; Max]	XX (XX) XX.X ± XX.X XX [XX ; XX]
Serum chemistries		
Creatinine	N (N Missing) Mean ± SD Median [Min ; Max]	XX (XX) XX.XX ± XX.XX XX.X [XX.X ; XX.X]
Uric acid	N (N Missing) Mean ± SD Median [Min ; Max]	XX (XX) XXX.X ± XXX.X XXX [XXX ; XXX]
Total bilirubin	N (N Missing) Mean ± SD Median [Min ; Max]	XX (XX) XX.XX ± XX.XX XX.X [XX.X ; XX.X]
Alkaline phosphatases	N (N Missing) Mean ± SD Median [Min ; Max]	XX (XX) XXX.X ± XXX.X XXX [XXX ; XXX]
LDH	N (N Missing) Mean ± SD Median [Min ; Max]	XX (XX) XXX.X ± XXX.X XXX [XXX ; XXX]
Total protein	N (N Missing) Mean ± SD Median [Min ; Max]	XX (XX) XX.X ± XX.X XX [XX ; XX]
Albumin	N (N Missing) Mean ± SD Median [Min ; Max]	XX (XX) XX.XX ± XX.XX XX.X [XX.X ; XX.X]
SGOT	N (N Missing) Mean ± SD Median [Min ; Max]	XX (XX) XXX.X ± XXX.X XXX [XXX ; XXX]

SGPT	N (N Missing) Mean ± SD Median [Min ; Max]	XX (XX) XXX.X ± XXX.X XXX [XXX ; XXX]
Calcium	N (N Missing) Mean ± SD Median [Min ; Max]	XX (XX) X.XXX ± X.XXX X.XX [X.XX ; X.XX]
Glycaemia	N (N Missing) Mean ± SD Median [Min ; Max]	XX (XX) X.XX ± X.XX X.X [X.X ; X.X]
Infectious disease surveillance		
CMV	Negative Positive Missing	n/N (XX.X%) n/N (XX.X%) n
EBV	Negative Positive Missing	n/N (XX.X%) n/N (XX.X%) n
Hepatitis B	Negative Positive Missing	n/N (XX.X%) n/N (XX.X%) n
Immunology		
Gammaglobulin level	N (N Missing) Mean ± SD Median [Min ; Max]	XX (XX) XX.XX ± XX.XX XX.X [XX.X ; XX.X]
Antinuclear antibody	Negative Positive Missing	n/N (XX.X%) n/N (XX.X%) n
ANCA	Negative Positive Missing	n/N (XX.X%) n/N (XX.X%) n
Cardiac assessment		
EKG – Performed?	Not realized Realized Missing	n/N (XX.X%) n/N (XX.X%) n
EKG – Result	Abnormal Normal Missing	n/N (XX.X%) n/N (XX.X%) n
QTc	N (N Missing) Mean ± SD Median [Min ; Max]	XX (XX) XXX.X ± XXX.X XXX [XXX ; XXX]
Serum levels of electrolytes		
Potassium	N (N Missing) Mean ± SD Median [Min ; Max]	XX (XX) X.XX ± X.XX X.X [X.X ; X.X]
Magnesium	N (N Missing)	XX (XX)

	Mean ± SD Median [Min ; Max]	X.XXX ± X.XXX X.XX [X.XX ; X.XX]
Results of other tests		
Performance status	0	n/N (XX.X%)
	1	n/N (XX.X%)
	2	n/N (XX.X%)
	3	n/N (XX.X%)
	4	n/N (XX.X%)
	Missing	n
Karnofsky index	N (N Missing)	XX (XX)
	Mean ± SD	XX.X ± XX.X
	Median [Min ; Max]	XX [XX ; XX]
Chest X ray	Not realized	n/N (XX.X%)
	Realized	n/N (XX.X%)
	Missing	n
If realized, chest X ray result	Abnormal	n/N (XX.X%)
	Normal	n/N (XX.X%)
	Missing	n
Cutaneous biopsy	Not realized	n/N (XX.X%)
	Realized	n/N (XX.X%)
	Missing	n
If realized, cutaneous biopsy result	Abnormal	n/N (XX.X%)
	Normal	n/N (XX.X%)
	Missing	n
% FEV1	N (N Missing)	XX (XX)
	Mean ± SD	XX.X ± XX.X
	Median [Min ; Max]	XX [XX ; XX]
Concomitant treatment		
Any concomitant treatments administrated?	No	n/N (XX.X%)
	Yes	n/N (XX.X%)
	Missing	n
Daily steroid dose (Prednisone) mg/kg/d	N (N Missing)	XX (XX)
	Mean ± SD	XX.X ± XX.X
	Median [Min ; Max]	XX [XX ; XX]
Daily cyclosporine dose	N (N Missing)	XX (XX)
	Mean ± SD	XX.X ± XX.X
	Median [Min ; Max]	XX [XX ; XX]

11.2.3 Signs and symptoms of cGvHD at baseline

Derivation

Derived variable	Definition
Liver score	
The liver score is defined as a combination of Total bilirubin, ALT (SGPT) and AP (ALK) as follows:
 
Score 0: Normal total bilirubin and ALT < 3 ULN and AP < 3 ULN
 
Score 1: Normal total bilirubin with ALT ≥ 3 to 5 ULN or AP ≥ 3 to 5 ULN
 
Score 2: Elevated total bilirubin (> 1 ULN) but ≤ 3 mg/dL or ALT ≥ 5 ULN or AP ≥ 5 ULN
 
Score 3: Elevated total bilirubin > 3 mg/dL
 
Missing if at least one missing serum chemistry

Involved sites number	Number of sites or organs with a score ≥ 1 at baseline (V1)

The following table will be presented:

Variable	Statistics / Modality	Safety Population (N = XX)
NIH scoring of cGVHD		
Scoring of chronic GVHD (NIH criteria)	
Score 0: Asymptomatic and fully active (ECOG 0, KPS or LPS 100%)
 
Score 1: Symptomatic, fully ambulatory, restricted only in physically strenuous activity (ECOG 1, KPS or LPS 80-90 %)
 
Score 2: Symptomatic ambulatory, capable of selfcare,
	
n/N (XX.X%)
 
n/N (XX.X%)
 
n/N (XX.X%)

	> 50 % of walking hours out of bed (ECOG 2, KPS or LPS 60-70 %)	
	Score 3: Symptomatic, limited self-care > 50 % of waking hours in bed (ECOG 3-4, KPS or LPS < 60 %)	n/N (XX.X%)
	Missing	n
Skin – Abnormalities present but explained entirely by non-GvHD documented cause	No	n/N (XX.X%)
	Yes	n/N (XX.X%)
	Missing	n
	Score 0: No BSA involved	n/N (XX.X%)
	Score 1: 1-18% BSA	n/N (XX.X%)
Skin score	Score 2: 19-50% BSA	n/N (XX.X%)
	Score 3: > 50% BSA	n/N (XX.X%)
	Missing	n
Mouth – Abnormalities present but explained entirely by non-GvHD documented cause	No	n/N (XX.X%)
	Yes	n/N (XX.X%)
	Missing	n
	Score 0: No symptoms	n/N (XX.X%)
	Score 1: Mild symptoms with disease signs but not limiting oral intake significantly	n/N (XX.X%)
Mouth score	Score 2: Moderate symptoms with disease signs with partial limitation or oral intake	n/N (XX.X%)
	Score 3: Severe symptoms with disease signs on examination with major limitation or oral intake	n/N (XX.X%)
	Missing	n

Lung – Abnormalities present but explained entirely by non-GvHD documented cause	No	n/N (XX.X%)
	Yes	n/N (XX.X%)
	Missing	n
Lung score + FEV1	Score 0: No symptoms	n/N (XX.X%)
	Score 1: Mild symptoms (shortness of breath after climbing one flight of steps)	n/N (XX.X%)
	Score 2: Moderate symptoms (shortness of breath after walking on flat ground)	n/N (XX.X%)
	Score 3: Severe symptoms (shortness of breath at rest: requiring 0)	n/N (XX.X%)
Eyes – Abnormalities present but explained entirely by non-GvHD documented cause	Missing	n
	No	n/N (XX.X%)
	Yes	n/N (XX.X%)
Eyes score	Missing	n
	Score 0: No symptoms	n/N (XX.X%)
	Score 1: Mild dry eye symptoms not affecting ADL	n/N (XX.X%)
	Score 2: Moderate dry eye symptoms partially affecting ADL without new vision impairment due to KCS	n/N (XX.X%)
Gastro-intestinal – Abnormalities present but	Score 3: Severe eye symptoms significantly affecting ADL or unable to work because of ocular symptoms of loss or vision due to KCS	n/N (XX.X%)
	Missing	n
	No	n/N (XX.X%)
Yes	Yes	n/N (XX.X%)

Gastro-intestinal score	explained entirely by non-GvHD documented cause	Missing	n
		Score 0: No symptoms	n/N (XX.X%)
		Score 1: Symptoms without significant weight loss (< 5 %)	n/N (XX.X%)
		Score 2: Symptoms associated with mild to moderate weight loss (5-15 %) OR moderate diarrhea without significant interference with daily living	n/N (XX.X%)
		Score 3: Symptoms associated with significant weight loss > 15 %, requires nutritional supplement for most calorie needs OR esophageal dilation OR severe diarrhea with significant interference with daily living	n/N (XX.X%)
Liver score	Liver – Abnormalities present but explained entirely by non-GvHD documented cause	Missing	n
		No	n/N (XX.X%)
		Yes	n/N (XX.X%)
		Missing	n
		Score 0: Normal total bilirubin and ALT or AP < 3 ULN	n/N (XX.X%)
		Score 1: Normal total bilirubin with ALT \geq 3 to 5 ULN and AP \geq 3 to 5 ULN	n/N (XX.X%)
		Score 2: Elevated total bilirubin (> 1 ULN) but ≤ 3 mg/dL or ALT ≥ 5 ULN or AP ≥ 5 ULN	n/N (XX.X%)
		Score 3: Elevated total bilirubin > 3 mg/dL	n/N (XX.X%)
Joint and fascia – Abnormalities present but	Missing	n	
	No	n/N (XX.X%)	

explained entirely by non-GvHD documented cause	Yes	n/N (XX.X%)
	Missing	n
	Score 0: No symptoms	n/N (XX.X%)
	Score 1: Mild tightness of arms or legs, normal or mild decreased range of motion (ROM) AND not affecting ADL	n/N (XX.X%)
	Score 2: Tightness of arms and legs OR joints contractures, erythema thought due to fasciitis, moderate decrease ROM AND mild to moderate limitation of ADL	n/N (XX.X%)
	Score 3: Contractures WITH significant decrease of ROM AND significant limitation of ADL (unable to tie shoes, button shirts, dress self, etc...)	n/N (XX.X%)
	Missing	n
Involved sites number		
Involved sites number	N (N Missing)	XX (XX)
	Mean ± SD	X.X ± X.X
	Median [Min ; Max]	X [X ; X]
Current patient weight		
Current patient weight (in kg)	N (N Missing)	XX (XX)
	Mean ± SD	XX.X ± XX.X
	Median [Min ; Max]	XX [XX ; XX]
Performance score		
Performance status	KPS	n/N (XX.X%)
	ECOG	n/N (XX.X%)
	LPS	n/N (XX.X%)
	Missing	n
If ECOG	ECOG 1	n/N (XX.X%)
	ECOG 2	n/N (XX.X%)
	ECOG 3	n/N (XX.X%)
	Missing	n
Chronic GVHD activity assessment - Clinician		
Overall GvHD severity	No GVHD	n/N (XX.X%)
	Mild	n/N (XX.X%)

	Moderate	n/N (XX.X%)
	Severe	n/N (XX.X%)
	Missing	n
Assessment of cGVHD severity (from 0 to 10)	N (N Missing)	XX (XX)
	Mean \pm SD	XX.X \pm XX.X
	Median [Min ; Max]	XX [XX ; XX]
Chronic GVHD activity assessment - Patient		
Assessment of cGVHD severity (from 0 to 10)	N (N Missing)	XX (XX)
	Mean \pm SD	XX.X \pm XX.X
	Median [Min ; Max]	XX [XX ; XX]

